11.1 Inclusion Criteria

Every eligible patient at participating investigational sites must meet the following criteria:

Inclusion criteria:

1. Male and female patients 18 years or older by the time of enrolment
2. Confirmed diagnosis of Crohn's disease or ulcerative colitis for at least 2 years prior to enrolment in the study.
3. The presence of a moderate to severe IBD flare at the time of enrolment or in patient anamnesis within 2 years before enrollment treated with steroids or/ and immunosuppressive agents or/ and biologic therapy. IBD flare(s) must be confirmed in the source documentation.
4. Current treatment with steroids or/ and immunosuppressive agents or/ and 5-ASA or/ and biologic therapy
5. Written informed consent, signed before the participation in the study begins.

11.2 Exclusion Criteria

Any patient who meets any of the following criteria will not be qualified for entry into the study:

1. Current or previous (within the last two years) indeterminate or not classified colitis.
2. Changing of IBD type in anamnesis (i.e. from UC to CD, etc) within the last two years.
3. Current, previous (within the last two years) or planned (for the next one year) participation in interventional clinical trial.
4. Presenting of mental incapacity, unwillingness or language barriers precluding adequate understanding or cooperation.
5. Any other condition, which on the opinion of the investigator may impact the patient's participation in the study.
6. Patient received previous treatment with biologic therapy/immunosuppressive agents for conditions other than IBD ever in their lifetime.

11.3 Justification for criteria inclusion and exclusion

The criteria are set to ensure a patient population that will enable the investigation of the set objectives.

As this is non-interventional observational study, we don't restrict exclusion criteria artificially. According to ethical rules, all patients must sign informed consent form before enrolling. Data erroneously collected from patient for which signed informed consent form is not available, will not be included in or will be deleted from the database.

Exclusion criteria were designed to prevent inclusion of patients with unconfirmed diagnosis, treated with investigational drugs or having mental disorders or a language barrier precluding adequate understanding or cooperation with the investigator and collection of the information required by the study protocol.

11.4 Patient selection and procedure for avoiding of selection bias

In order to reduce selection bias, each patient who is planned for study enrolment has to be documented in an anonymous patient log file (independent of prescribed treatment and signing of the Informed Consent Form) in a consecutive manner at each site.

Eligible patients must be enrolled consecutively into the study and documented in the case report form. Not eligible patient must be skipped. In case a patient is not eligible (e.g. no informed consent signed), the reason for non-eligibility must be documented in the patient log file.

11.5 Discontinuation/withdrawal of patients from the study

11.5.1 Criteria for Discontinuation or Withdrawal of a patient

Patients may be discontinued from the study at any time, based on investigator decision. Specific reasons for discontinuing a patient from the study are:

1. Voluntary withdrawal of informed consent in patient's request or at the request of patient's legally acceptable representative.

The patient (or patient's legally acceptable representative) wishes to withdraw from the study. The reason for withdrawal, if provided, should be recorded in the eCRF. Note: All attempts should be made to determine the underlying reason for the withdrawal and, where possible, the primary underlying reason should be recorded (i.e., withdrawal due to an AE or lack of efficacy should not be recorded in the "voluntary withdrawal" category).

2. Development of exclusion criteria during the study.
3. Adverse Events (AE)/ Serious Adverse Events (SAE), including Patient's death

The patient has experienced an AE or SAE that requires early termination because patient is unwilling to continue because of the AE or SAE, or continuation of patients' visit to the clinic is impossible or any other occurrence which can be happened.

4. Protocol deviations and incorrect enrolment of the patient. The investigator and the sponsor will decide whether there is a deviation from the protocol.
5. Lost for observation within the framework of the study. The patient did not return to the clinic and attempts to contact the patient were unsuccessful.
6. Study termination. Sponsor decision or regulatory authorities' requirement about cessation of the study.
7. Other (specify)

If the patient is lost for observation within the study length and it is impossible to conduct the final visit; the investigator must do its best to get in touch with the patients for getting full information and clarifying the reasons. The attempts to contact patient should be documented.

Details for the premature termination of the study/sites as a whole are provided in section 10.5 (Premature termination or Suspension of Study or Investigational Site).

11.5.2 Replacement

Patients will not be replaced after drop out.

11.5.3 Procedures for Discontinuation or Withdrawal of a patient

There are no special procedures of discontinuation of patients. The investigator may terminate a patient's study participation at any time during the study when the patient meets the study termination criteria described above in Section 11.5.1. In addition, patient/legal representative may discontinue participation in the study without giving a reason at any time during the study.

In all cases, the reason for withdrawal must be recorded in the eCRF and in the patient's medical records. The patients who prematurely withdrew from the study are not replaced with new ones, and their data will be included into the final analysis. In case if investigator loses contact with the patient during the study observation, the investigator may contact with the patient directly or through the other health care professionals who observe this patient in routine practice. In that case part of eCRF "End of observation" can be filled in basing on data received via e-mails/calls.

12 Data collection

12.1 Data source

Data collection should be started only after Informed Consent Form is signed by the investigator and patient. A unique patient identification number (patient number) will be assigned to each patient at the time that informed consent is obtained; this patient number will be used throughout the study. Source data will include medical records or other sources of information (e.g. laboratory tests forms, validated copies of medical summaries given by other specialists etc.).

12.2 Tabulated overview of data collection

The documentation of study data will be reported by investigators via electronic case report form (eCRF).

Assessment / Procedure	Retrospective data collection*	Baseline visit (V1, Day 1)	Observational visit (V2, Month 6)	Final visit (V3, Month12)
Informed consent		X		
Patients' eligibility assessment: Inclusion/exclusion criteria		X		
Date of visit		X	X	X
Demographics data		X		
Disability		X		
Physical examination		X	X	X
Medical history / Concurrent medical conditions	X	X		
History of IBD	X	X		
IBD family history		X		
IBD assessment	X	X	X	X
Disease activity data		X	X	X
IBD status		X	X	X
Laboratory and instrumental evaluation of IBD **	X	X	X	X
IBD treatment	X	X	X	X
Healthcare resources utilization	X	X	X	X
Concomitant treatment		X	X	X
Physician Survey		X		X
Adverse events			X	X

* Retrospective data within two years before of patient enrolment in the study will be collected at Visit 1 after the signing of the informed consent form

**All examinations (laboratory tests and instrumental exams) are done in accordance with clinical routine practice and physician's decision. All examinations results should be registered in electronic CRF only if they are done in routine practice.

12.3 Data collected on the Baseline visit (V1), including collection of Retrospective data within two years before of patient enrolment in the study

The baseline visit takes place at the physician's office. Data to be collected:

- Date of Informed consent form signing (day, month, year);
- Inclusion/exclusion criteria;
- Date of visit (day, month, year);
- Demographics data (gender, date of birth, ethnicity, region of residence, smoking status, employment status (employed, unemployed, retired, student, other));
- Disability:
 - Disability group
 - Cause of disability
 - Year of disability
- Physical examination: height (cm) and weight (kg), body mass index calculation;
- Medical history/Concurrent medical conditions (disease, date of diagnosis, resolution date);
- History of inflammatory bowel disease (IBD):
 - Type of inflammatory bowel disease (ulcerative colitis (UC) or Crohn's disease (CD)),
 - Date of IBD diagnosis,
 - Date of IBD symptoms onset,
 - Availability of observation in the current investigational site within previous 2 years
- IBD family history (degree of relationship);
- Clinical course of IBD (acute, chronic continuous, chronic recurrent);
- IBD assessment for the last 2 years and at the time of the baseline visit:
 - Disease extent according to the following Montreal Classification categories;
 - Systemic (extra intestinal) IBD manifestations;
 - IBD complications;
 - Vaccination in accordance with IBD treatment guidelines.
- Disease activity data at baseline visit will consist of specified signs and symptoms depending on the disease type:
 - CD: abdominal pain severity, number of liquid stools per day, presence of an abdominal mass, endoscopic findings (if done), documented presence of CD

complications, and Harvey Bradshaw Index or other documented disease activity scales (if applicable).

- UC: frequency of stools/day, rectal bleeding, endoscopic findings (if done), physician global assessment of disease severity, and Mayo scores or other documented disease activity scales (if applicable).
- IBD status at baseline visit:
 - IBD status as judged by investigator (remission, incomplete remission, flare, others), nature of remission at the time of examination;
 - IBD flare(s);
- Laboratory and instrumental evaluation of IBD for the last 2 years and at the time of the baseline visit (if done within routine practice) - for details please section 12.8;
- IBD treatment:
 - IBD treatment for the last 2 years and at the time of the baseline visit;
 - IBD surgical treatment for the last 2 years and at the time of the baseline visit;
- Healthcare resources utilization for the last 2 years and at the time of the baseline visit;
- Concomitant treatment.

12.4 Data collected at the Observational visit (V2) and Final Visit (V3)

Data to be collected directly on Observational visit (V2) and Final visit (V3):

- Date of visit (day, month, year)
- Type of visit: visit to physician office or distant contact
- Physical examination: weight (kg), body mass index calculation;
- IBD assessment at the time of the visit:
 - Disease extent according to the following Montreal Classification categories;
- Disease activity data at the visit will consist of specified signs and symptoms depending on the disease type:
 - CD: abdominal pain severity, number of liquid stools per day, presence of an abdominal mass, endoscopic findings (if done), documented presence of CD complications, and Harvey Bradshaw Index or other documented disease activity scales (if applicable).
 - UC: frequency of stools/day, rectal bleeding, endoscopic findings (if done), physician global assessment of disease severity, and Mayo scores or other documented disease activity scales (if applicable).
- IBD status (with current/last available data by the date of the visit):

- IBD status as judged by investigator (remission, incomplete remission, flare, others), nature of remission at the time of examination;
- IBD flare(s);
- Systemic (extra intestinal) IBD manifestations;
- IBD complications;
- Vaccination in accordance with IBD treatment guidelines.
- Laboratory and instrumental evaluation of IBD (if done within routine practice) - for details please section 12.8;
- IBD treatment;
- IBD surgical treatment;
- Healthcare resources utilization;
- Concomitant treatment
- Adverse events and adverse drug reactions (seriousness, severity, causality, start and stop dates, action, frequency, outcomes):
 - adverse drug reactions on IBD treatments,
 - adverse events on Entivyo® (Vedolizumab) treatment,
 - serious adverse events on IBD treatments (including Entivyo® (Vedolizumab) treatment).

All adverse events and adverse drug reactions must be documented on the Adverse Report Form which is appended to the Case Report Form.

12.5 Data collected at the End of observation

The end of observation in this study should be documented for all patients who passed the Baseline visit.

The following data on the eCRF titled “End of Observation” should be documented:

- Date of the last contact,
- Type of the last contact,
- Prematurely discontinuation of study visits (data collection) – yes/no,
- Reason(s) for discontinuation of prematurely data collection (if applicable).

12.6 Treatments to be documented in the study

12.6.1 IBD treatment

Due to non-interventional design of the study, the decision about particular IBD treatment strategy to the patient is taken by treating physician. All IBD medications are not provided by Sponsor.

Following medications for IBD treatment should be registered in eCRF; 5-ASA, immunosuppressive agents (including azathioprine (AZA), 6-mercaptopurine (6-MP), methotrexate (MTX), cyclosporine A), corticosteroids and biologics.

The following data should be documented for steroids:

- INN name;
- release form;
- Route of administration
- Indication
- start date;
- initial and maximum daily dose;
- funding source;
- dose, if continued / end date and the reason for modification/ discontinuation, if discontinued.

The following data should be documented for 5-ASA, immunosuppressive agents:

- INN name;
- release form;
- Route of administration
- Indication start date;
- daily dose;
- funding source;
- continued / end date and the reason for modification/discontinuation.

The following data should be documented for biologics:

- trade and INN name;
- Indication start date;
- treatment regimen (induction or supportive care);
- dosage regimen;
- Route of administration
- funding source;
- continued / end date and the reason for modification/discontinuation.

If a physician takes a decision to change something from the above it must be documented in the eCRF.

12.6.2 Concomitant medication

Concomitant medication is any drug given in addition to the IBD treatment. These drugs may be prescribed by a physician or obtained by the patient over the counter.

It is not planned to collect full data about concomitant medication in this study. In present study only concomitant medication clinically relevant to the opinion of investigator are collected. Areas of Takeda's interest are:

- Therapy of tuberculosis (including prevention of tuberculosis),
- IBD extra intestinal manifestations (EIMs) therapy.

The information about concomitant medication can be received both on base of medical records and on questions to patients (according to routine practice). During the visits the information about changes in the concomitant therapy is recorded. At each study visit, patients will be asked whether they have taken any medication other than medication for IBD treatment used from signing of informed consent through the end of the study.

For every drug there will be documented INN, trade name, dosage regimen (single and total daily dose), duration of treatment (start and stop dates) and indication, frequency, route of administration.

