**Table 1 Tabulated overview of visits and procedures**

The documentation of study data will be reported by investigators via electronic case report form (eCRF).

Assessment / Procedure	Retrospective data collection*	Baseline visit (V1, Day 1)	Observational visit (V2, Month 6)	Final visit (V3, Month12)
Informed consent		X		
Patients' eligibility assessment: Inclusion/exclusion criteria		X		
Date of visit		X	X	X
Demographics data		X		
Disability		X		
Physical examination		X	X	X
Medical history / Concurrent medical conditions	X	X		
History of IBD	X	X		
IBD family history		X		
IBD assessment	X	X	X	X
Disease activity data		X	X	X
IBD status		X	X	X
Laboratory and instrumental evaluation of IBD **	X	X	X	X
IBD treatment	X	X	X	X
Healthcare resources utilization	X	X	X	X
Concomitant treatment		X	X	X
Physician Survey		X		X
Adverse events			X	X

\* Retrospective data within two years before of patient enrolment in the study will be collected at Visit 1 after the signing of the informed consent form

\*\*All examinations (laboratory tests and instrumental exams) are done in accordance with clinical routine practice and physician's decision. All examinations results should be registered in electronic CRF only if they are done in routine practice.

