### **8.7 Interim analysis**

Two interim analyses are planned – in 2019 and 2020 – with corresponding interim data locks for the completed cases:

- 2019: about 700 completed cases for retrospective data analysis
- 2020^2: 3000 completed cases for retrospective and partial prospective data (up to 6 months)

---

 According to the current version of the protocol, the set of collected data has been reduced to 2000 cases. Therefore, the second analysis (second look) of data was not performed in 2020.

Protocol ID	MACS-2017-102279	STATISTICAL ANALYSIS PLAN	Page 30 of 41	
IP	N/A		Date	30.12.2021
ID	MACS-2017-102279_SAP		Version	v1.2 final

All cases will be included into interim analysis with the prerequisite of complete data cleaning, i.e., corresponding eCRF forms are complete, free of any pending queries and signed by the corresponding investigator.

Retrospective data analysis (2019): will include the following endpoints (all endpoints will be assessed retrospectively for the period of 2 years of retrospective data collection):

- 1) Treatment patterns associated with prior biologic agents use or non- biological therapy according to the algorithm provided in the section 8.1.2);
- 2) Demographic data, medical history, treatment history, concurrent diseases, concomitant medications by treatment group/pattern;
- 3) Demographic data for FAS;
- 4) Family history of IBD, smoking habits, medical history comorbidities for FAS;
- 5) Disease characteristics: age of disease onset, location of disease, clinical course, disease severity, intestinal and systemic (extraintestinal) manifestations, complications in history for FAS;
- 6) Frequency and methods of assessment of UC/CD disease activity;
- 7) Assessment of healthcare resource utilization;
- 8) TB incidence and prevalence in IBD patients by treatment pattern;
- 9) TB medication's use in IBD patients by treatment pattern;
- 10) Compliance between the assessment of IBD status by investigator and objective methods of assessment (Mayo index, Harvey-Bradshaw index, instrumental assessments).

No safety analysis will be performed for the retrospective data analysis as there will be no safety data in the retrospective part of the study.

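### SAP 8.7 places TB-medication and concomitant-drug use in a 2-year retrospective analysis, but no text requires a non-IBD drug stopped before consent to be recorded

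*Protocol*

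**What the plan says.** **What is to be reported.** SAP 8.7 describes the 2019 interim analysis (about 700 completed cases) as one in which "all endpoints will be assessed retrospectively for the period of 2 years of retrospective data collection". Its list of endpoints includes concomitant medications by treatment group or pattern (item 2) and "TB medication's use in IBD patients by treatment pattern" (item 9). The 2020 interim list repeats both items, but a footnote in the same section says that this analysis was not performed.

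**What is to be collected.**
- Protocol 12.6.2 names TB treatment and TB prevention as one of two areas of interest within concomitant medication. It says that "It is not planned to collect full data about concomitant medication in this study". At each visit, patients are asked about "any medication other than medication for IBD treatment used from signing of informed consent through the end of the study". It also says that "The information about concomitant medication can be received both on base of medical records and on questions to patients", and that start and stop dates are recorded for each drug.
- In Protocol 12.2 and SAP Table 1, the row "Concomitant treatment" is marked at V1, V2 and V3 and is blank in the retrospective column. The rows for IBD treatment, laboratory and instrumental evaluation, and healthcare resource use are marked in that column.
- The V1 data list (Protocol 12.3, SAP 5.3.1) includes "IBD treatment for the last 2 years and at the time of the baseline visit". It gives the same look-back to surgery, laboratory and instrumental data, and healthcare resource use. Its concomitant-treatment entry has none.
- SAP 5.3.3 lists concomitant treatment among the data gathered continuously through the prospective year.

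**The concern.** The reporting window and the collection window differ. Item 9 asks for TB-drug use over the 2 years before enrolment, but the drugs that supply it are requested only from consent onward. A course that ran and finished within those 2 years falls between the two.

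The likely result is a percentage that is too low. The shortfall need not be equal across treatment patterns: the earlier in the look-back a course fell, the more likely it was over by V1. If TB prevention is timed around the start of a biologic (an assumption), patterns with earlier biologic starts would lose more courses, and item 9 is a tabulation by pattern.

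There is also an asymmetry with TB testing. Protocol 12.7 collects TB diagnostic tests retrospectively. A patient could therefore appear with a positive test and no TB drug merely because the course was completed before consent. A reader might take that for a gap in care, and Protocol 5.2 says the study is meant to help reveal gaps. Therapy for extraintestinal manifestations, the other named area of interest, has the same problem under item 2.

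**Working it through.** The plan states no figure for TB-drug use, so there is nothing to reproduce. The check has two parts: whether the missing data could enter by another route, and how large the loss could be.

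**1. Routes by which a TB drug stopped before consent could be recorded**

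| Possible route | What the documents provide |
|---|---|
| Concomitant treatment, retrospective column | Blank (Protocol 12.2, SAP Table 1) |
| Concomitant treatment at V1 | Listed, with no look-back (Protocol 12.3, SAP 5.3.1) |
| Question to the patient | From consent onward (Protocol 12.6.2) |
| IBD treatment, 2-year look-back | 5-ASA, immunosuppressants, corticosteroids and biologics only (Protocol 12.6.1) |
| Medical history | Diseases and their dates, not drugs (Protocol 12.3, 12.8) |
| Medical records as a source | Allowed, with no look-back period and no requirement (Protocol 12.6.2) |
| Prior medications | A coding rule in SAP 8.1.1; no data list collects them |

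No route requires the record; the last two permit it at most. A drug still running at consent is recorded with its pre-consent start date, so the loss is confined to courses that ended before consent.

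**2. Illustration of size (every input is an assumption except the 24 months and the 700 cases)**

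Suppose one course of L months per treated patient, with its start uniform over the 24 months before V1. It is still running at V1 if it began within the last L months, so P(recorded) = L/24:
- L = 3: 3/24 = 12.5%
- L = 6: 6/24 = 25%
- L = 9: 9/24 = 37.5%
- L = 12: 12/24 = 50%

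The share missed is 1 − L/24, which runs from 87.5% down to 50%.

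For scale, take 700 cases and an assumed true use of 20%: 700 × 0.20 = 140 users. The table would show 140 × L/24 = 17.5, 35, 52.5 and 70 users, or 2.5%, 5%, 7.5% and 10% of 700.

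**3. A limit of that formula**

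L/24 counts only courses that began inside the window. Use over 2 years also includes courses already running when the window opened. If starts are uniform over the 24 + L months before V1, every course that touches the window is counted and the share still running at V1 is L/(24 + L): 3/27 = 11.1%, 6/30 = 20%, 9/33 = 27.3%, 12/36 = 33.3%. The direction is the same and the recorded share is smaller. Neither version is an estimate for this study.

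**The case against.** The strongest reply is that the 2-year statement in SAP 8.7 is loose. It also covers demographics, family history and smoking, and agreement of the investigator's IBD status with the activity indices. Disease activity and IBD status have no retrospective mark either. On this reading the phrase means data available at the V1 lock, and items 2 and 9 promise no 2-year percentage. That is a fair reading, but the SAP does not state it, and a table built from the text as written would carry the 2-year label.

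Second, the consent-onward sentence governs what patients are asked. Records are an allowed source, start and stop dates are kept, and the SAP expects to code prior medications, so some sites may record earlier courses. The eCRF and the SAP example tables were not available for this review, so actual capture cannot be verified. This stands: the data are not required, which is less than saying they are never collected. Uneven recording between sites would still leave a 2-year percentage hard to interpret.

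Third, limited collection of concomitant drugs is a declared choice. That justifies collecting little; it does not support reporting over a longer period than was collected.

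Two stronger readings are tempting, and the documents support neither.
- *Patients with completed prevention are counted as untreated.* No classification rule is given. SAP 8.1.1 bases percentages on non-missing observations, and SAP 8.1.4 annotates tables with missing ones. Such counting is plausible, because a drug that is not asked about may leave no missing field and SAP 8.4 plans no assessment of missing-data patterns. It remains an inference.
- *The TB objective is undermined.* The TB outcomes in Protocol 6.2, SAP 7.3 and SAP 8.1.3 are positive tests or active TB before biologics, and reactivation or new occurrence. None uses TB medication, and none undertakes to separate patients with and without prevention.

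**Conclusion.** The mismatch is real, and its reach is limited. As written, SAP 8.7 items 2 and 9 report concomitant-drug and TB-drug use over 2 retrospective years, and no text requires a non-IBD drug stopped before consent to be recorded. A 2-year TB-medication percentage would probably be too low.

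The size cannot be computed from the documents, which give neither course lengths nor a rate of use. The illustrative recorded share of 12.5% to 50% rests on assumed courses of 3 to 12 months, uniform starts over 24 months, and no site recording completed courses from the records. Any such recording would reduce the loss.

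The explicit 2-year window belongs to the 2019 interim analysis, and the 2020 analysis was not performed. No primary, secondary, safety or listed exploratory outcome changes. What is at risk is the reading of a descriptive table, and of any later TB-drug or concomitant-drug table that carries the same window forward.

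**What to change.** **If collection is still open:** in Protocol 12.2 and 12.6.2 and in SAP Table 1, mark TB therapy and prevention in the retrospective column. Record yes, no or unknown with start and stop dates, transcribed at V1 from records already being reviewed. The unknown category keeps absence of information apart from absence of treatment. Cost: one small eCRF item.

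**If collection is closed:** restrict SAP 8.7 items 2 and 9, and any final TB-drug or concomitant-drug table, to drugs ongoing at V1 or started afterwards. Label the tables so, and report no 2-year TB-medication percentage. Cost: a wording change and a less complete descriptive table.

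The second option is probably the relevant one. Protocol 10.2 planned the last patient visits for Q2–Q3 2021 and the end of data collection for Q3–Q4 2021, and SAP v1.2 is dated 30.12.2021.
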